### Exploratory Endpoints

[figure not shown]
- Values and changes from baseline in humoral and cellular immunogenicity data including P467-specific antibodies (IgG), Her 2-specific antibodies (IgG), vaccine-specific cytokine levels and regulatory and effector T and B cells
- Values and changes from baseline in serum and biochemical markers of tumor progression
- Values and changes from randomization in Her-2-specific antibodies (IgG) inhibition of in-vitro tumor cell growth
- Values and changes from baseline in intra-tumor T cells and biochemical markers from pre- and post-treatment tumor biopsies

### Safety Endpoints

- Incidence of treatment-emergent adverse events (TEAE), Grade 3 or higher TEAEs, serious TEAEs, and TEAEs leading to study treatment discontinuation
- Incidence of treatment-emergent grade 3/4 clinical laboratory abnormalities
- Changes and shifts from baseline in clinical laboratory, vital signs, and electrocardiogram (ECG) parameters
- Change from baseline in ECOG performance grade
- Concomitant medication use
- Treatment compliance

## 4. General Statistical Considerations

### 4.1. Reporting Convention

### 4.2. Analysis Window

[figure not shown]
Baseline is defined as the last non-missing measurement prior to the first administration of any study treatment. For patients who were randomized but not treated, baseline will be the assessment taken on or before the randomization visit Baseline/ Day 0.

The day of the first dose of any study drug will be defined as study Day 0. Study day are calculated relative to Day 0, as the difference between the date of interest and Day 0.

[figure not shown]
For the post-baseline by-visit summaries of safety assessments, the nominal visits as captured on the eCRF page will be utilized.

For the purpose of by-visit summaries of efficacy assessment (like the change in tumor size) and humoral immunogenicity data, the post-baseline visit mapping rules described in [Table 4-1](#) and [Table 4-2](#) will be used respectively. When multiple records fall in the same post-baseline visit window, the record with the study day closest to the target visit day will be chosen. In a case of a tie, the record with the earlier date will be chosen. Records that not chosen will be effectively

treated similarly to an unscheduled assessment and will still be included in all except the by-visit summaries.

#### **4.3. Sample Size Calculation**

#### **4.4. Randomization, Stratification, and Blinding**

Patients will be randomized using a permuted block randomization in a 1:1 ratio to receive IMU-131 plus chemotherapy or chemotherapy alone treatment. Randomization will be performed centrally using an Interactive Voice or Web Response System (IxRS) and stratified by tumor stage at screening (III vs. IV).

Phase 2 is an open-label study in which all the personnel will be unblinded except for the central radiography reviewers.

#### **4.5. Analysis Set**

The following analysis sets will be used:

ITT Set: All randomized patients. Patients will be analyzed as randomized. This analysis set will be used for primary efficacy analysis.

Evaluable Set (EVAL): All randomized patients who receive any amount of study treatment and have at least one evaluable post-baseline tumor response. Patients will be analyzed as randomized.

The Full Analysis Set (FAS): All randomized patients who receive any amount of study treatment. FAS analyses will be conducted on the basis of the randomized treatment.

Safety Set: All randomized patients who receive any amount of study treatment. Patients will be analyzed as treated. All the safety analyses will be based on the Safety set.

Per-protocol (PP) Set: A subset of the ITT set who will be selected based on the study drug experience (compliance and/or time on study drug) and major protocol deviations. The criteria for inclusion in the PP set will be finalized and documented prior to data base lock. Patients will be analyzed as randomized.

## 5. Patient Disposition

### 5.1. Disposition

A summary of patient's disposition will be presented based on the ITT set. The number and percentage of patients who received at least one dose of study treatment, and who discontinued study treatment will be presented by treatment group and in total, with specific primary reasons for treatment discontinuation presented as well. A similar summary will be repeated for study discontinuation.

The enrollment will be summarized by study site and treatment group.

The number and percentage of patients included in each analysis set will be provided. All the percentages will be based on the number of patients randomized.

A Listing of patient treatment and study disposition will be provided.

### 5.2. Protocol Deviations

The protocol deviations will be defined in a separated study deviation rules document and will be identified and assessed by clinical research investigators or designee throughout the study. Any major protocol violation will be assessed prior to database lock, and to be considered for exclusion from Per-protocol Set. The number and percentage of subjects with major protocol deviations will be summarized overall and for each treatment group by type of deviation based on the ITT set. A listing of protocol deviations will be provided.

## 6. Demographics and Baseline Characteristics

The demographics and baseline characteristics will be summarized by treatment group and in total based on the ITT set. No inferential statistics will be presented. Individual patient listings will be provided to support the summary tables.

### 6.1. Demographics

Descriptive statistics for the following demographic variables will be provided:

- Age at consent (years)
- Gender (Male, Female)
- Primary race (Blank or African American, American Indian or Alaska Native, Asian, Native Hawaiian or other Pacific Islander, White, Other, Not reported)
- Ethnicity (Hispanic or Latino, Not Hispanic or Latino, Not reported, Unknown)
- Height (cm)
- Weight (kg)
- Body mass index (BMI; kg/m^2): calculated as (weight in kilograms) / (height in meters)

### 6.2. Baseline Disease Characteristics and Prior Gastric Cancer Therapy

Descriptive statistics for the following disease characteristics will be provided:

- Baseline ECOG performance status
- Baseline left ventricular ejection function (LVEF)
- Initial tumor diagnosis type (Adenocarcinoma of gastroesophageal junction, Adenocarcinoma of the stomach)
- Disease Extent at Initial Diagnosis (Resectable, Borderline Resectable, Unresectable locally advanced, Unresectable and metastatic)
- Tumor stage at screening (Stage III, Stage IV)
- Gross location of primary tumor (Type I, II, III, Not applicable)
- Time since the initial diagnosis (in days): calculated as date of informed consent – date of initial diagnosis + 1. If either month or month and day of initial diagnosis date is missing, use the January 1. If day is missing, use the first day of the month. Imputation will not be done for completely missing date.
- Number of target lesions at baseline
- Sum of lesion diameters (mm) of target lesions at baseline according to RECIST 1.1

The number and percentage of patients with prior gastric cancer therapy will be summarized as below:

- Prior gastric cancer surgery (yes, no)
- Prior gastric cancer drug therapy (yes, no)

- Prior gastric cancer radiotherapy (yes, no)

Listings of prior gastric cancer surgery, prior gastric cancer drug therapy and prior gastric cancer radiotherapy will be provided, presenting the detail information captured on the specific eCRF pages.

### **6.3. Medical History**

Medical history will be coded according to the Medical Drug Regulatory Activities (MedDRA), version 21.0 or higher. A frequency summary of medical history will be provided by system organ class (SOC) and preferred term (PT).

## 7. Treatments and Medications

### 7.1. Prior and Concomitant Medications

Medications reported on the Prior and Concomitant Medications eCRF pages will be coded using World Health Organization Drug Dictionary (WHODD) March 2019 version and grouped into relevant categories based on the Anatomical Therapeutic Chemical (ATC) coding scheme.

A prior medication is defined as any medication taken prior to the first administration of any study treatment (i.e. intake was stopped prior to the first administration). A concomitant medication is defined as any medication that is ongoing on/after the first administration or taken on/after the first administration.

For the purpose of inclusion in prior and/or concomitant medication tables, incomplete medication start and stop dates will be imputed as described in [Appendix 2](#).

If start date is completely missing and end date is not prior to the first dose, then the medication will be classified as concomitant. If the start date is completely missing and the end date is prior to the first dose of study drug, then the medication will be classified as prior. If the end date is completely missing, then the medication will be classified as concomitant. Medications for which both the start and end dates are completely missing will be classified as both prior and concomitant.

The number and percentage of patients with any prior medications will be summarized by ATC level 3 and generic drug name for each treatment group and in total. Similar frequency tables will be provided for concomitant medications. All summaries will be performed using the Safety set.

A listing of prior and concomitant medications will be provided.

### 7.2. Concomitant Procedures/Surgeries

Concomitant procedure/surgery will be coded using the MedDRA version 21.0 or higher. A concomitant procedure/surgery is defined as any procedure/surgery conducted on or after the first administration of study treatment. Procedure/surgery with a missing date will be classified as concomitant.

The number and percentage of patients with any concomitant procedure/surgery will be summarized by SOC and PT for each treatment group and in total using the Safety set.

A listing of concomitant procedure/surgery will be provided.

### 7.3. Study Treatments

#### 7.3.1. Extent of Exposure

The treatment duration is defined as time interval in weeks between the date of first administration of any study treatment and the treatment end date inclusive, calculated as  $(\text{treatment end date} - \text{date of the first administration of any study treatment} + 1) / 7$ . The treatment end date will be the date of last IMU-131 injection if applicable, or the date of last chemotherapy treatment captured on the End of Treatment eCRF page, whichever is later. For patients who are still treatment ongoing at the clinical cutoffs, the treatment end date will be

earlier date of the clinical cutoff date and the maximum date among the exposure data captured on the IMU-131 Vaccination eCRF pages if applicable, and the specific Chemotherapy administration eCRF pages.

Descriptive summary of treatment duration will be provided by treatment group. The total number of vaccinations, and the total number of cycles of chemotherapy administrated per patient will be summarized descriptively by treatment group. All summaries will be performed using the Safety set.

[figure not shown]
[figure not shown]
### **7.3.2. Treatment Compliance**

The treatment compliance of IMU-131 vaccination will be calculated as the actual total number of vaccinations administrated divided by the prescribed number of vaccinations up to the disease progression or the data cutoff date and then multiplying 100. The acceptable range for compliance is defined as between 80% - 100%.

Treatment compliance will be summarized descriptively and categorically in terms of < 80% and  $\geq 80\%$  to  $\leq 100\%$ .

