6.5. Patient Withdrawal

6.5.1. Main discontinuation criteria

Patients will discontinue study treatment and complete the study according to the study protocol when there is documented evidence of disease progression according to RECIST 1.1 response criteria or if unacceptable toxicity occurs. Patients may discontinue study treatment and be withdrawn from the study prematurely based on symptomatic clinical disease progression without documented radiographic evidence only after discussion with the Sponsor/medical monitor.

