6.5.2. Contraindications to repeated vaccination

If any of the following adverse events arise during the study they constitute contraindications to further administration of IMU-131, and patients should discontinue IMU-131 treatment permanently and be withdrawn from the study immediately, with appropriate safety follow-up by the investigator until resolution of the event, as with any adverse event (see [Section 9: Adverse Event Reporting](#)):

- Anaphylactic reaction following the administration of vaccine(s).
- Any clinically relevant immunosuppressive or immuno-deficient condition.

The following events constitute contraindications to administration of IMU-131. If an adverse event, the event must be reported and the patient followed as with any adverse event. Withdrawal of patients experiencing the following events is at the discretion of the investigator as indicated below:

- Acute illness at the time of vaccination. Acute illness is defined as the presence of a moderate or severe illness with or without fever. All vaccines can be administered to persons with a minor illness such as diarrhea, mild upper respiratory infection with or without low-grade febrile illness, i.e., temperature $<38^{\circ}\text{C}$. Withdrawal is at the discretion of the investigator if acute illness will not resolve in sufficient time to allow for vaccination schedule to continue.
- Temperature $\geq 38^{\circ}\text{C}$ at the time of vaccination. Withdrawal is at the discretion of the investigator if raised temperature will not resolve in sufficient time to allow for vaccination schedule to continue.

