9.9. Pregnancy

Patients who become pregnant during the study period and up to at least 28 days following chemotherapy or 180 days after the last dose of IMU-131 must not receive additional doses of IMU-131 but may continue other study procedures at the discretion of the investigator.

Patients should be instructed to notify the investigator if it is determined after completion of the study that they or their partner (male patients) became pregnant either during the study or within 28 days following chemotherapy or 180 days after the last dose of IMU-131.

If a pregnancy occurs within 28 days following chemotherapy or 180 days after the last dose of IMU-131, the pregnancy should be followed to term, any premature terminations reported, and the health status of the mother and child including date of delivery and the child's gender and weight should be reported to Imugene Limited after delivery. The mother may freely choose to terminate the pregnancy as her own decision. Neither the Sponsor nor investigators should influence this decision in any way. Similarly, neither the investigators nor Sponsor have the right to intervene or influence

this decision and any ensuing procedures. If this occurs, the termination of pregnancy should be considered an elective surgical procedure and any associated adverse events attributed accordingly.

If the outcome of the pregnancy meets the criteria for an SAE (ie, ectopic pregnancy, spontaneous abortion, intrauterine fetal demise, neonatal death, or congenital anomaly [in a live born, a terminated fetus, an intrauterine fetal demise, or a neonatal death]), the investigator should follow the procedures for reporting SAEs.

Investigational Product: IMU-131
Protocol Identifier: IMU.ACS.001
Protocol Version: Protocol Global Amendment #5, 27 September 2023

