#### Treatment Period

Patient who are determined to be eligible for the study will be randomized on the Baseline/Day 0 visit. Treatment for both groups will begin at the Baseline/Day 0 visit.

Patients in the IMU-131 plus chemotherapy group will receive vaccination of IMU-131 at Baseline/Day 0, Day 14, Day 35, Day 77, Day 140 and then every 63 days until disease progression. Patients in both the IMU-131 plus chemotherapy group and the chemotherapy alone group will receive chemotherapy starting at the Baseline/Day 0 visit and then every 21 days for a maximum of 6 cycles as clinically indicated or until disease progression, whichever occurs sooner. Chemotherapy will be consisting of:

- Cisplatin by intravenous administration at 80 mg/m^2 on the first day of each cycle and either 5-FU, 4000 mg/m^2 CIV (administered as 1000 mg/m^2/day as continuous infusion for 96 hours on days 1 to 4 of each cycle) or capecitabine for 14 days at 2000 mg/m^2/day, orally (administered as 1000 mg/m^2 twice daily morning and evening for a total of 2000 mg/m^2/day on days 1 to 14 of each cycle);
- Or oxaliplatin, by intravenous administration at 130 mg/m^2 on Day 1 of each cycle and capecitabine for 14 days at 2000 mg/m^2/day, orally (administered as 1000 mg/m^2 twice daily morning and evening for a total of 2000 mg/m^2/day on days 1 to 14 of each cycle).

Patients who withdraw from the treatment or have progressive disease will undergo the End of Treatment (EoT) assessments as planned in the [Schedule of Study Procedures](#).

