## 8.2. Secondary Efficacy Endpoint

### 8.2.1. Progression-free Survival (PFS)

PFS is defined as time in days from the randomization to the date of disease progression or death due to any cause on or prior to the clinical cutoff date, whichever occurred earlier. The disease progression will be defined as the radiological disease progression as assessed by blinded central reviewers. Therefore, duration of PFS in days is defined as the time between the date of randomization and the date of the first occurrence of one of the following events:

- Radiological disease progression per RECIST 1.1 as assessed by the blinded central reviewers, i.e. a tumor response of PD is observed
- Death due to any cause

The calculation of PFS is a two steps process.

- Determination of date of disease progression, which is the date of assessment corresponding to the first date time that overall tumor response is “Progressive Disease” on the Overall Tumor Response-RECIST eCRF
- Calculation of duration from randomization to disease progression, death, or censoring date as described in [Table 8-1](#) as follows. In cases where a patient’s tumor is downstaged to become surgically resectable, this is considered a response to treatment with subsequent surgery being part of the patient’s normal clinical care. Such cases are considered evaluable PFS event at time of confirmed progressive disease.

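### The vaccination compliance formula has no end point for death or a protocol-required vaccine stop, so read literally it counts doses that could not be given

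*SAP*

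**What the plan says.** SAP Section 7.3.2 defines compliance as the number of vaccinations administered "divided by the prescribed number of vaccinations up to the disease progression or the data cutoff date and then multiplying 100". On the range it adds: "The acceptable range for compliance is defined as between 80% - 100" per cent. Results are to be shown descriptively and in two categories, below 80% and 80% to 100%.

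The schedule that supplies the prescribed number is in SAP Section 3.1 (Treatment Period): Day 0, Day 14, Day 35, Day 77, "Day 140 and then every 63 days until disease progression".

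The protocol ends vaccination without progression in several situations:

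- Section 6.5.1: study treatment stops at RECIST progression "or if unacceptable toxicity occurs".
- Section 6.5.2: after an anaphylactic reaction or a clinically relevant immunosuppressive or immunodeficient condition, "patients should discontinue IMU-131 treatment permanently and be withdrawn from the study immediately".
- Section 9.9: patients who become pregnant "must not receive additional doses of IMU-131 but may continue other study procedures at the discretion of the investigator".

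SAP Table 8-1 has its own rows for death before documented progression and for treatment discontinuation due to symptomatic deterioration. The SAP therefore foresees these patients.

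**The concern.** The formula names two end points, progression and data cutoff. The schedule does not end the count any sooner, because it too runs until progression. A patient who dies without progression therefore keeps accruing due doses to the cutoff. So does a patient whose vaccine must be stopped permanently and who has not progressed. The numerator is frozen while the denominator grows, and the score falls with calendar time for reasons unrelated to adherence.

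Treatment compliance is a listed Phase 2 safety endpoint (SAP Section 3.2). Compliance and/or time on drug is also a stated basis for choosing the per-protocol set (SAP Section 4.5). The measure applies to the vaccine arm only. An early death or a required stop would be reported there as poor adherence.

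**Working it through.** The plan gives no numerical compliance result, so there is no figure to reproduce. The check applies the Section 7.3.2 ratio to the schedule.

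**Inputs**

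- Scheduled days (SAP Section 3.1): 0, 14, 35, 77, 140, then 203, 266, 329, 392, 455, 518, 581 and so on in steps of 63.
- Doses due by a cutoff, counted from the patient's own Day 0: 5 by Day 140, 6 by Day 240, 7 by Day 300, 8 by Day 365, 11 by Day 540, 12 by Day 600.
- Day of death or stop, and day of cutoff: assumptions, shown over a range. In every case the patient has no progression and received every dose due before the stop.

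**Formula as written:** 100 × doses given / doses scheduled up to cutoff. **Alternative:** 100 × doses given / doses scheduled up to the death or stop.

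| Death or stop | Given | Cutoff | As written | Count ended at stop |
|---|---|---|---|---|
| Day 0, after first dose | 1 | Day 365 | 1/8 = 12.5% | 1/1 = 100% |
| Day 60 | 3 | Day 300 | 3/7 = 43% | 3/3 = 100% |
| Day 60 | 3 | Day 600 | 3/12 = 25% | 3/3 = 100% |
| Day 100 | 4 | Day 140 | 4/5 = 80% | 4/4 = 100% |
| Day 100 | 4 | Day 365 | 4/8 = 50% | 4/4 = 100% |
| Day 100 | 4 | Day 540 | 4/11 = 36.4% | 4/4 = 100% |
| Day 150 | 5 | Day 240 | 5/6 = 83.3% | 5/5 = 100% |
| Day 150 | 5 | Day 365 | 5/8 = 62.5% | 5/5 = 100% |
| Day 210 | 6 | Day 240 | 6/6 = 100% | 6/6 = 100% |

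**When the category changes.** The score drops below 80% once 1 unavailable dose is counted for a patient with 1 to 3 doses given, 2 for 4 to 7 doses, and 3 for 8 to 11 doses. If no scheduled dose falls between stop and cutoff, nothing changes.

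**Plausible gaps.** SAP Section 3.1 plans 22 months of recruitment and 8 months of follow-up. If those timings hold, even the last patient recruited is about 8 × 30 = 240 days from randomization at the final cutoff, by which 6 doses are scheduled. Death on Day 60 would then score 3/6 = 50% for that patient, and less for anyone enrolled earlier.

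**Weight of one patient.** With about 36 patients at 1:1, the vaccine arm has about 18. Each misclassified patient moves a category percentage by 1/18 = 5.6 points.

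**The case against.** The best defence is the word *prescribed*. A dose that the protocol forbids, or one falling after death, is arguably not prescribed, and then the formula is already right. That reading is possible. But the SAP does not state it, it names its two end points explicitly, and Section 7.3.1, just before, defines a treatment end date that Section 7.3.2 does not use. Two programmers could derive different values. Some SAP text is not visible in the public copy (Sections 4.1 and 13, and figures near Section 7.3.1). A supplementary rule there cannot be excluded, although the Section 7.3.2 sentence reads as complete.

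A second defence is that few patients are affected. The protocol synopsis reports no IMU-131-related safety signals or dose-limiting toxicities in the 36-patient Phase 2, so vaccine stops for toxicity may be rare. This stands, and the documents do not allow the number of affected patients to be estimated. It does not cover death without progression.

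A reader might also infer three stronger points that the documents do not support:

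- **Scores above 100%.** SAP Section 8.2.1 says "The disease progression will be defined as the radiological disease progression as assessed by blinded central reviewers". If that date ended the denominator on Day 126 and the site gave the Day 140 dose, the score would be 5/4 = 125%, which fits neither category. But that definition belongs to PFS. Sections 8, 8.2.6 and 8.2.8.1 also use investigator-assessed or site-recorded progression. Section 8.2.5 cross-refers to Section 8.2.1 when it wants that definition, and Section 7.3.2 does not. With the progression that ends vaccination, the example is 5/5. If the limit governs the numerator as well, it is 4/4. What remains is that Section 7.3.2 does not name its progression source.
- **Delivered dosing misreported.** Section 7.3.1 summarises vaccinations per patient and treatment duration, and Section 5.1 tabulates reasons for discontinuation. These are correct whatever Section 7.3.2 does.
- **Biased efficacy results.** OS and PFS are analysed by ITT (Protocol Section 10.4.2). The per-protocol set is optional, its criteria are to be finalised before database lock, and no rule using the 80% limit exists.

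**Conclusion.** The point holds in a limited form. Followed literally, Section 7.3.2 gives a wrong value for a vaccine-arm patient who dies, or whose vaccine must be permanently stopped, without progression, whenever at least one scheduled dose falls before the cutoff. For an individual the error can be large: 43% or 25% in place of 100% for the Day 60 example. It is small or absent when the stop comes late relative to the cutoff. These sizes rest on assumed stop and cutoff days and on full dosing before the stop.

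The consequence is a misstated descriptive safety endpoint in one arm. An effect on the per-protocol set is conditional on compliance becoming a criterion. This is worth correcting because the rule is explicit and the repair is short. It is not a threat to the primary or PFS analysis.

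**What to change.** In SAP Section 7.3.2:

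1. End the denominator at the earliest of the progression that stops vaccination, death, a permanent vaccine stop required by the protocol, and data cutoff.
2. State that progression here means the site-recorded date, since that is what governs vaccination.
3. Apply the same end date to the numerator, so that the ratio fits the two stated categories, and say how doses given within a visit window are matched to scheduled days.
4. Do not let voluntary withdrawal end the denominator unless those patients are reported separately. It may be true non-adherence, and a patient who took one dose and left would otherwise score 1/1 = 100%.

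The cost is a few lines of SAP text and one derivation, using dates that should already be collected. The small downside is that compliance would no longer reflect required stops, but these remain visible in the discontinuation table of Section 5.1. The change takes no position on the clinical stopping rules themselves.
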